#### 6.1.5 Medical History and Current Medical Conditions

Counts and percentages for medical history and current medical conditions will be presented for each body system of participants using ITT analysis set. General medical history, previous *Clostridioides difficile* infection, and liver/cardiovascular related medical conditions will be summarized separately in tables and listings. A distinct summary table will also be produced for history of previous uncomplicated UTIs during the past 3 months, past 3-6 months, past 6-12 months, and past 5 years, and pre-existing conditions with similar symptoms in past 12 months for the ITT analysis set and primary clinically evaluable at 24 hours ( $\pm 4$  hours) analysis set. All data will be listed.

#### 6.1.6 Study Intervention Compliance

[figure not shown]
A summary of overall compliance and compliance up to each timepoints of CSS assessments from start of gepotidacin treatment based on the exposure data will be produced. Counts & percentages for below categories as applicable will be presented using safety and CE24 set.

- <80%
- $\geq 80\% - <100\%$
- =100%

- $\geq 100\%$

Overall Compliance rate (%) will be calculated as per following formula:

CCI

Compliance rate (%) upto each visit/timepoint will be calculated as per following formula:

CCI

### 6.1.7 Additional Analyses Due to the COVID-19 Pandemic

No additional analysis will be performed due to COVID-19 pandemic.

## 6.2 Appendix 2 Electronic Clinical Outcome Assessment (eCOA) Compliance

Not Applicable.

## 6.3 Appendix 3 Data Derivations Rule

### 6.3.1 Criteria for Potential Clinical Importance

#### 6.3.1.1 ECG

ECG Parameter	Units	Potential Clinically Important Range	
		Lower	Upper
Absolute			
Absolute QTc Interval	msec	NA	>450
Absolute PR Interval	msec	<110	>220
Absolute QRS Interval	msec	<75	>110

### 6.3.1.2 Vital Signs

Vital Sign Parameter (Absolute)	Units	Potential Clinically Important Range	
		Lower	Upper
Systolic Blood Pressure	mmHg	<85	>160
Diastolic Blood Pressure	mmHg	<45	>100
Pulse Rate	bpm	<40	>110
Temperature	C	$\leq 35$	$\geq 38$
Respiratory Rate	bpm	<10	>20

### 6.3.2 Laboratory Values

For this study, Division of AIDS [DAIDS, 2017] for Grading the Severity of Adult and Pediatric Adverse Events defined in Section 6.3.11 will be utilized. This differs from the EAGLE-2 and EAGLE-3 phase III studies, where AE grading was done using the Division of Microbiology and Infectious Diseases (DMID) table, which is no longer used.

### 6.3.3 Study Period

Assessments and events will be classified according to the time of occurrence relative to the study intervention period.

Study Period	Definition
CCI	

#### 6.3.3.1 Study Period for Concomitant Medication

Study Period	Definition
Prior	If medication started prior to the first dose date (or ICF date if first dose date is missing)
Concomitant	If medication ended after the first dose date or is ongoing regardless of the start date (or ICF date if first dose date is missing)

#### NOTES:

- Please refer Section 6.3.8 for handling of missing and partial dates for concomitant medication. Use the rules which is mentioned in table of Section 6.3.8 if concomitant medication date is completely missing.
- If a participant has taken single medication on the same date as the first dose date, then time will be used to determine if it's prior or concomitant. If time is missing, it will be considered concomitant.

### 6.3.4 Treatment Emergent Flag for Adverse Events

Flag	Definition
Treatment Emergent	If adverse event (AE) onset date/time is on or after treatment start date/time, i.e., study intervention starts date/time $\leq$ adverse event (AE) starts date/time. If time is missing, only date will be compared.

**NOTES:**

[figure not shown]
Time of study intervention dosing and start/stop time of adverse events (AEs) should be considered, if collected.

### 6.3.5 Study Day and Reference Dates

The safety reference date is the study intervention start date and will be used to calculate study day for safety measures.

[figure not shown]
The efficacy reference date is the study intervention start date and will be used to calculate study day for efficacy measures and baseline characteristics, as well as efficacy durations.

The study day is calculated as below:

### 6.3.6 Assessment Window

CCI

For adverse events (AEs) and concomitant medications, study data will not be reported by visit as this assessment are collected through the study.

Analysis timepoint labels will be assigned to each post-baseline record (including records from unscheduled and early termination timepoints where date/time is collected for safety data Labs, ECG, Vitals etc.) based on the corresponding study hours/day (relative to first study intervention).

Descriptive summaries that are shown for “any assessment post baseline” e.g., maximum/minimum/worst case post baseline, will use all assessments irrespective of whether they fall in an analysis timepoint window and irrespective of whether they are scheduled or unscheduled.

**Table 3 Analysis Assessment Window for Post-Baseline**

Timepoints Analysis Set / Domain	Protocol Visit Window/ Extended Visit Window	Target	Analysis Timepoint Window	
			Beginning Timepoint	Ending Timepoint
Efficacy (Primary, Secondary and Exploratory)	24 hours $\pm$ 4 hours	24 hours	$\geq$ 20 hours	$\leq$ 28 hours
	24 hours $\pm$ 12 hours		$>$ 12 hours	$\leq$ 36 hours
	48 hours $\pm$ 4 hours	48 hours	$\geq$ 44 hours	$\leq$ 52 hours
	48 hours $\pm$ 12 hours		$>$ 36 hours	$\leq$ 60 hours
	72 hours $\pm$ 4 hours	72 hours	$\geq$ 68 hours	$<$ 76 hours
	72 hours $\pm$ 12 hours		$>$ 60 hours	$\leq$ 84 hours
	96 hours $\pm$ 4 hours	96 hours	$\geq$ 92 hours	$\leq$ 100 hours
	96 hours $\pm$ 12 hours		$>$ 84 hours	$\leq$ 108 hours
CCI				

If multiple records exist within the same analysis timepoint window, then the record occurring closest to the target hours/day will be utilized in all analyses and analysis set determinations. If multiple records are equally close to the target hours/day, then the later record will be utilized. If multiple records occur on the same hours/day and time is not collected, then the record with the larger Study Data Tabulation Model (SDTM) record sequence number will be utilized in all analyses. All protocol assessments (including unscheduled and early termination timepoints) will be presented in participant listings. Both the nominal and analysis timepoint will be presented in listings.

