**Table 1 Clinical outcome at each Visit/Timepoint**

Definition Criteria	Outcome
Improvement of clinical signs and symptoms of uUTI present from Baseline, but not complete resolution, without the participant receiving other systemic antimicrobials for uUTI on/before each timepoint and without receiving other systemic antimicrobials for any other infections before each timepoint.	Clinical Improvement without Clinical Resolution
Improvement and complete resolution of clinical signs and symptoms of uUTI present from Baseline, without the participant receiving other systemic antimicrobials for uUTI on/before each timepoint and without receiving other systemic antimicrobials for any other infections before each timepoint.	Clinical Improvement with Clinical Resolution
Resolution of clinical signs and symptoms of uUTI present at Baseline (i.e., reduction of total CSS score to 0), without receiving other systemic antimicrobials for uUTI on/before each timepoint and without receiving systemic antimicrobials for other infections before each timepoint.	Clinical Resolution
No change is a change from baseline score of 0 at each timepoint, without the participant receiving other systemic antimicrobials for uUTI on/before each timepoint and without receiving systemic antimicrobials for other infections before each timepoint.	No Change
Worsening in clinical signs and symptoms from baseline (i.e., increase from baseline total CSS score $\geq 1$ ) and/or the participants receiving other systemic antimicrobials for uUTI on/before each timepoint.	Clinical Worsening
(1) The baseline score is missing, (unless clinical worsening outcome criteria were met) or (2) Post baseline assessment is missing (unless clinical worsening outcome criteria were met): 
 
• The post-baseline visit occurred but assessment is missing, or
 
• The post-baseline visit not occurred, or
 
	Unable to determine

Definition Criteria	Outcome

 
The post-baseline assessment is out of visit window, or
 
 
(3) The participant received any other systemic antimicrobials for other infections before the post-baseline timepoint (unless clinical worsening outcome criteria were met)
	

Note: Each timepoint is defined based on the date/time from the first dose.

Timepoints are 24 hours  $\pm$  4 hours, 48 hours  $\pm$  4 hours, 72 hours  $\pm$  4 hours, 96 hours  $\pm$  4 hours.

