### 4.2.1. Definition of primary endpoint

The primary efficacy endpoint is achieving clinical symptom improvement (including clinical resolution). In this study, a participant will be considered to have clinical improvement (including clinical resolution) outcome if they attain either a “Clinical Improvement with Clinical Resolution” outcome or, a “Clinical Improvement without Clinical Resolution” outcome as defined in Table 1. And otherwise, as not improved/failure if they have any other outcomes.

Individual scores will be recorded by a study physician or otherwise appropriately medically trained staff, as recorded in the delegation log. Clinical symptom score (CSS) of acute cystitis participants will be recorded as per the protocol defined SoA using the following scoring system:

Clinical Signs and Symptoms	None	Mild  Symptom is easily tolerated, causing minimal discomfort, and not interfering with everyday activities	Moderate  Symptom is sufficiently discomforting to interfere with normal everyday activities	Severe  Symptom prevents normal everyday activities
	SCORE 0	SCORE 1	SCORE 2	SCORE 3
Dysuria a				
Frequency				
Urgency				
Lower abdominal				

Clinical Signs and Symptoms	None	Mild	Moderate	Severe
	SCORE 0	SCORE 1	SCORE 2	SCORE 3
or suprapubic pain				

a. Dysuria is defined as pain or burning when passing urine.

- The clinical signs and symptoms include dysuria, frequency, urgency, and lower abdominal or suprapubic pain. Each of the signs and symptoms will be scored from 0 to 3.
- At Baseline, the participant must present with at least 2 signs and symptoms and have a total cumulative symptom score  $\geq 2$ . The total cumulative symptom score is derived by summing the score for each individual sign and symptom. If any individual sign and symptom scores are missing, then total symptom score will also be missing. If the participant is missing baseline assessment, they will be considered 'Unable to determine' (refer [Table 1](#)) for outcome at the respective visit.
- The clinical symptoms improvement will be programmatically determined by comparing the total scores of the signs and symptoms of acute cystitis at the 24 hours ( $\pm 4$  hours) to those present at baseline as shown in [Table 1](#).

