### 6.3.10 Handling of Missing Data

Element	Reporting Detail
General	
 
Missing data occurs when any requested data is not provided, leading to blank fields on the collection instrument:           
 
These data will be indicated using a “blank” in participant listing displays. Unless all data for a specific visit are missing in which case the data is excluded from the table.
 
Answers such as “Not applicable” and “Not evaluable” are not considered to be missing data and should be displayed as such.
 
 
 

Efficacy	
 
As defined in the endpoint variables, participants with missing measurements will be treated as failures for corresponding visits (unless otherwise specified for sensitivity analyses).
 

Outliers	
 
Any participants excluded from the summaries and/or statistical analyses will be documented along with the reason for exclusion in the clinical study report.
 

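### SAP Table 3 closes the 72 h ±4 h window at <76 h, so a symptom score taken at exactly 76 h meets the endpoint definition but is counted as a failure

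*SAP*

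**What the plan says.** SAP Section 6.3.7 builds the analysis visits from the windows in Section 6.3.6, which are set out in Table 3. The efficacy block of that table begins "Efficacy (Primary, Secondary and Exploratory" and gives each time point a ±4 h row and a ±12 h row. Among the ±4 h rows, those for 24, 48 and 96 h run from ≥20 to ≤28, ≥44 to ≤52 and ≥92 to ≤100 h. The 72 h row runs from ≥68 to <76 h.

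The 72 h improvement and resolution endpoints (SAP Sections 1.1 and 4.3.1), the CE72 set (SAP Section 3) and the note under SAP Table 1 all use 72 hours ±4 hours, with no strict upper limit.

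Three provisions settle what happens to a score outside its window:

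- Table 1 lists "The post-baseline assessment is out of visit window" among the reasons for the outcome Unable to determine, unless the worsening criteria are met.
- Section 4.2.1 classifies every outcome that is not an improvement: "And otherwise, as not improved/failure if they have any other outcomes". Section 4.3.1 repeats this rule for 48, 72 and 96 h, and counts Unable to determine as not resolved.
- Section 6.3.10 adds that "participants with missing measurements will be treated as failures for corresponding visits", except where a sensitivity analysis specifies otherwise.

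**The concern.** Table 3 is what a programmer will code. One of its eight ±4 h limits is strict, which contradicts both its sister rows and the endpoint definition. A participant who was called on time by the protocol's own window, and who had improved or become symptom-free, would be reported as a failure at 72 h because of an inequality sign. The note under Table 1 would accept the same score. Two programmers working independently could therefore classify it differently, each following a table in the SAP.

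At stake are the 72 h improvement and resolution rates, which are secondary endpoints. The primary endpoint at 24 h is not touched, because its row ends inclusively at 28 h.

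**Working it through.** **Step 1. Compare each ±4 h row with its definition.**

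| Time point | Target ±4 h | Table 3 start | Table 3 end | Is target +4 h inside? |
|---|---|---|---|---|
| 24 h | 20 to 28 h | ≥20 | ≤28 | yes |
| 48 h | 44 to 52 h | ≥44 | ≤52 | yes |
| 72 h | 68 to 76 h | ≥68 | <76 | **no** |
| 96 h | 92 to 100 h | ≥92 | ≤100 | yes |

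With the limits coded as printed, 28, 52 and 100 h each fall inside their ±4 h row. So does 75.99 h for the 72 h row. At exactly 76 h a score is outside the 72 h ±4 h row, although 72 + 4 = 76 and the 72 h ±12 h row (>60 to ≤84 h) contains it.

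**Step 2. Follow a CSS at 76.0 h that shows improvement, with no other antimicrobial and no other record between 68 and 76 h.**

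- It meets 72 ±4 h in the endpoint definition.
- Under Table 3 it is out of window, so Table 1 gives Unable to determine.
- Section 4.3.1 then counts it as not improved and, if the score was 0, as not resolved.
- CE72 membership does not change. If the score is treated as available, doses before 76.0 h count. If it is treated as missing, doses before 72 + 4 = 76 h from first dose count. The cut-off is the same, so the participant stays in the denominator as a failure.

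A participant with no change or with worsening at 76.0 h is a failure either way. The strict sign can therefore only lower the 72 h rates.

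**Step 3. Size.** The protocol synopsis plans at least 82 evaluable participants, for a 95% CI half-width of about 10% or less at a 74% rate. The exact (Clopper-Pearson) interval reproduces this: 82 is the smallest n with a half-width at or below 10% (9.97%, taking 0.74n as the count). That figure does not depend on the present point and serves only as a scale.

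The documents do not give the size of CE72, so it is assumed here:

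- With 82 participants, one affected improver moves the rate by 1/82 = 1.2 points.
- With all 90 planned participants, the shift is 1/90 = 1.1 points.
- As an illustration at the planning rate, 61/82 = 74.4% (95% CI 63.6 to 83.4) becomes 60/82 = 73.2% (62.2 to 82.4).
- With no score at exactly 76.0 h, nothing changes.

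If times are kept to the minute (an assumption), the inclusive window holds 8 × 60 + 1 = 481 distinct times, and the strict sign removes one of them.

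**The case against.** The strongest reply is that this is a typographical slip. It concerns a single instant and secondary endpoints only, and the ±4 h definition already shows the intent. All of that stands as to size. It does not remove the point, because Table 3 is an operative rule and is wrong as printed. No redaction bears on the sign.

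A reader might infer something larger: that Table 3 gives the primary endpoint two competing windows, since the ±4 h and ±12 h rows share one efficacy label, and that the choice could be made after the data are seen. The documents do not support this, for four reasons:

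- The column header separates the two as "Protocol Visit Window/ Extended Visit Window". The ±4 h windows are nested inside the ±12 h ones.
- The visible endpoint definitions, the CE sets, the Table 1 note and the main analyses (SAP Sections 1.1, 3, 4.1.3, 4.2.2 and 4.3.1.2) all use ±4 h. On that text, a CSS at 30 h is a failure in the main primary analysis.
- The rule for the ±12 h rows may lie in redacted text. The opening of Section 6.3.6 is redacted, as are parts of the version history and of Sections 3, 4.6 and 4.8. Its absence from view is not a gap in the plan.
- The words "then the record occurring closest to the target hours/day will be utilized in all analyses and analysis set determinations" belong to a rule for choosing among several records within one window. They do not say which window an analysis uses.

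**Conclusion.** The point holds for the 72 h row only. As printed, Table 3 excludes a CSS at exactly 76.0 h that the endpoint includes, and the SAP's own rules then count it as a failure for 72 h improvement and resolution. The numerical effect is very small: about 1.2 points per affected improver if CE72 has 82 participants, and most likely none or very few are affected. The documents do not say how many scores will fall at that instant.

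The larger inference about the primary window should not be drawn. If k of 82 participants had scores outside ±4 h but inside ±12 h and 74% of them had improved, the two windows would differ by 0.74k/82, which is 1.8, 3.6 or 7.2 points for k = 2, 4 or 8. Those figures need an assumed k, and they need the primary analysis to use ±12 h against the visible text. They do not measure an error in the plan.

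**What to change.** In SAP Table 3, change the ending time point of the 72 h ±4 h row from <76 to ≤76 hours, and match the sign in the programming specification. This is a one-character edit with no effect on sample size, data collection or conduct.

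An optional clarity edit, which does not correct a defect, is to mark in Table 3 that the ±4 h rows govern the primary and secondary analyses and the CE24, CE48, CE72 and CE96 sets, and to name whichever analyses use the ±12 h rows. It costs a label or footnote in the same table.

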### 6.3.7 Multiple measurements at One Analysis Time Point

Analysis visits will be created based on visit windows as described in Section 6.3.6.

Handling of multiple CSS assessment - If a second assessment of CSS is taken on any specific day corresponding to 24h, 48h, 72h, 96h after taking CCI due to tolerability issues, the former assessment (taken before the CCI use) will be considered for reporting.

All assessments (including unscheduled and early termination visits) will be presented in participant listings. The arithmetic mean of the three recorded ECG measurements will be presented at baseline as described in Section 4.5.4.3.

If multiple assessments are taken from the same type of lab parameters from the same visit, then worst case will be used.

### 6.3.8 Handling of Missing and Partial Dates

Element	Reporting Detail						
General	
 
Partial dates will be displayed as captured by the in-participant listing displays.
 
However, where necessary, display macros may impute dates as temporary variables for sorting data in listings only. In addition, partial dates may be imputed for 'slotting' data to study phases or for specific analysis purposes as outlined below.
 
						
Adverse Events	
 
The eCRF allows for the possibility of partial dates to be recorded for AE start and end dates; that is, the day of the month may be missing. In such a case, the following conventions will be applied for calculating the time to onset and the duration of the event:
 
						
	
 
 Missing start day	 
If study intervention start date is missing (i.e., participant did not start study intervention), then set start date = 1st of month.
 
Else if study intervention start date is not missing:
 
 
If month and year of start date = month and year of study intervention start date, then 
 
If stop date contains a full date and stop date is earlier than study intervention start date, then set start date= 1st of month.
 
Else set start date = study intervention start date.
 
 
 
 
Else set start date = 1st of month.
 
In this case, event is considered On-treatment and treatment emergent as per Section 6.3.4.
 	
 
 Missing start time	 
Midnight 0:00:00 will be used for AEs with missing start time to determine if it's AChE-I
 
 
Treatment start time will be used for AEs with missing start time if treatment start date is same as AEs start date.
 
 	
 
 	 
If study intervention start date is missing (i.e. participant did not start study intervention), then set start date = January 1.
 
Else if study intervention start date is not missing:
 
 
If year of start date = year of study intervention start date, then 
 
If stop date contains a full date and stop date is earlier than study intervention start date, then set start date = January 1.
 
 
 
 	
 
	Missing start day	
If study intervention start date is missing (i.e., participant did not start study intervention), then set start date = 1st of month.
 
Else if study intervention start date is not missing:
 
 
If month and year of start date = month and year of study intervention start date, then 
 
If stop date contains a full date and stop date is earlier than study intervention start date, then set start date= 1st of month.
 
Else set start date = study intervention start date.
 
 
 
 
Else set start date = 1st of month.
 
In this case, event is considered On-treatment and treatment emergent as per Section 6.3.4.
	Missing start time	
Midnight 0:00:00 will be used for AEs with missing start time to determine if it's AChE-I
 
 
Treatment start time will be used for AEs with missing start time if treatment start date is same as AEs start date.
 
		
If study intervention start date is missing (i.e. participant did not start study intervention), then set start date = January 1.
 
Else if study intervention start date is not missing:
 
 
If year of start date = year of study intervention start date, then 
 
If stop date contains a full date and stop date is earlier than study intervention start date, then set start date = January 1.
 
 
 

Missing start day	
If study intervention start date is missing (i.e., participant did not start study intervention), then set start date = 1st of month.
 
Else if study intervention start date is not missing:
 
 
If month and year of start date = month and year of study intervention start date, then 
 
If stop date contains a full date and stop date is earlier than study intervention start date, then set start date= 1st of month.
 
Else set start date = study intervention start date.
 
 
 
 
Else set start date = 1st of month.
 
In this case, event is considered On-treatment and treatment emergent as per Section 6.3.4.
						
Missing start time	
Midnight 0:00:00 will be used for AEs with missing start time to determine if it's AChE-I
 
 
Treatment start time will be used for AEs with missing start time if treatment start date is same as AEs start date.
 
						
	
If study intervention start date is missing (i.e. participant did not start study intervention), then set start date = January 1.
 
Else if study intervention start date is not missing:
 
 
If year of start date = year of study intervention start date, then 
 
If stop date contains a full date and stop date is earlier than study intervention start date, then set start date = January 1.
 
 
 
						

Element	Reporting Detail					
		
 
– Else set start date = study intervention start date.
 
 
Else set start date = January 1.
 
In this case, event is considered On-treatment and treatment emergent as per Section 6.3.4.
				
	Missing end day	
Last day (dependent on the month and year example '28/29/30/31') of the month will be used will be used for the day, unless this is after the stop date of study treatment; in this case the study treatment stop date will be used.
				
	Missing end day and month	
No Imputation will be applied in case of AE with missing end day and month
				
	Missing end time	
23:59 will be used for AEs with missing time
				
	Completely missing start/end date	
 
• Completely missing start or end dates will remain missing, with no imputation applied. Information on AE occurred before, after, or on the same day as the study intervention will be used.
 
• Consequently, time to onset and duration of such events will be missing.
 
• Adverse events with entirely missing or unknown start dates will be assumed to be on-treatment and treatment emergent for reporting.
 
				
Concomitant Medications including Antibiotics and Prohibited medications/Medical History	
 
• Partial dates for any concomitant medications recorded in the CRF will be imputed using the following convention and the recorded partial date will be displayed in listings:
 
 
 
 Missing start day	 
If study intervention start date is missing (i.e. participant did not start study intervention), then set start date = 1st of month.
 
Else if study intervention start date is not missing:
 
 
• If month and year of start date = month and year of study intervention start date, then 
 
– If stop date contains a full date and stop date is earlier than study intervention start date, then set start date= 1st of month.
 
– Else set start date = study intervention start date.
 
 
 
 
Else set start date = 1st of month.
 	
 
 Missing start time	 
Midnight 0:00:00 will be used for concomitant medications with missing start time if treatment start date is not same as the concomitant medication start date.
 	
 
		Missing start day	
If study intervention start date is missing (i.e. participant did not start study intervention), then set start date = 1st of month.
 
Else if study intervention start date is not missing:
 
 
• If month and year of start date = month and year of study intervention start date, then 
 
– If stop date contains a full date and stop date is earlier than study intervention start date, then set start date= 1st of month.
 
– Else set start date = study intervention start date.
 
 
 
 
Else set start date = 1st of month.
	Missing start time	
Midnight 0:00:00 will be used for concomitant medications with missing start time if treatment start date is not same as the concomitant medication start date.

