#### **4.5.2.1.3. Acetylcholinesterase Inhibition (AChE-I) AESIs**

Any reported AE listed in AChE-I TOI listing with a start time no later than 12 hours after the last dose administered, as evaluated by the investigator as per the [DAIDS, 2017] grading criteria provided in protocol Section 10.10 and Appendix 10: Division of AIDS table for grading the severity of adult and pediatric AEs, version 2.1, July 2017, will be included in the programmatic identification of AChE-I related AESI. The most current version of MedDRA will be used as applicable at the time of this study SAC.

Cumulative grade score of Acetylcholinesterase-Inhibition (AChE-I) will be calculated as the sum of the grade of each reported AE. This enables the number of AEs and the severity of each AE to be considered. The grading scale is defined as

Cumulative Grade:	0	1	2	3	4
Cumulative Grade Score:	0	1 to 3	4 to 6	7 to 10	≥11

For instance, if a participant reports two AEs, one of Grade 1 and the other of Grade 3 their cumulative grade score of 4 would result in cumulative grade 2. This will be calculated for all AChE-I events, non-GI AChE-I events and GI AChE-I events. This will be calculated for All AChE-I events, non-GI AChE-I events and GI AChE-I events which will be summarized.

Acetylcholinesterase inhibition AESIs will be listed and tabulated by system organ class (SOC) and preferred term (PT) and maximum grade. Non-GI AChE-I events will also be

summarized. A separate table will summarize the AChE-I AESI by the number of events and unique preferred terms. In addition, time of onset (time from first dose to the onset of first event in hours), duration, and lag time (the time from last dose to the end date/time of the last event for subjects whose end date/time of the last event is after treatment end date/time) of AChE-I events will also be summarized, and repeated for non-GI AChE-I and GI AChE-I events.

AChE-I events with a start time less than 6 hours after the latest dose administered will also be flagged in listings.

Additionally, Adverse Events of Torsade de Pointes/QT Prolongation SMQ by PT will also be summarized based on the SMQs listed in the OPS. The most current version of MedDRA will be used as applicable at the time of this study SAC.

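### For an AE with an end month but no end day, SAP 6.3.8 can impute an end before onset or outside the recorded month, and can fix the AChE-I lag by the clock time of the last dose

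*SAP*

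**What the plan says.** SAP 6.3.8 allows partial AE dates and says that "the following conventions will be applied for calculating the time to onset and the duration of the event". These are therefore analysis rules, not only aids for sorting listings.

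- **End day missing:** the last day of the recorded end month, "unless this is after the stop date of study treatment; in this case the study treatment stop date will be used".
- **End time missing:** "23:59 will be used for AEs with missing time".
- **End day and month missing:** "No Imputation will be applied in case of AE with missing end day and month".
- **Start or end date wholly missing:** left missing. "Consequently, time to onset and duration of such events will be missing".

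SAP 4.5.2.1.3 counts a listed event as an AChE-I event of special interest if it occurs "with a start time no later than 12 hours after the last dose administered". It plans summaries of time of onset, duration and lag, repeated for GI and non-GI events. The last measure is defined as "lag time (the time from last dose to the end date/time of the last event", and is taken only "for subjects whose end date/time of the last event is after treatment end date/time".

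Treatment is ten doses over 5 or 6 calendar days (Protocol 6.1). AEs are collected until Visit 7 at Day 28 (Protocol 8.4.1).

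**The concern.** The cap at treatment stop has no lower limit at AE onset and no check that the stop date lies in the recorded end month. Neighbouring rules in SAP 6.3.8 behave differently. The AE start-day rule looks at the AE stop date before imputing, and the concomitant-medication end-day rule uses month-end without a treatment-stop cap. An AE with less information (day and month both missing) is left alone, while one with a known month can receive a date that contradicts that month.

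The rule also works against the lag measure. Lag is meant to show how long AChE-I events outlast treatment, yet the imputed end cannot be later than the day treatment stopped. Continuous summaries report minimum and maximum (SAP 4.1.1), so a single negative duration could appear as a table minimum. With about 90 participants, few may contribute to lag.

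**Working it through.** The documents give no figure on this point, so there is none to reproduce. The rule was applied literally.

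**Formulas.** Imputed end E = the earlier of (last day of recorded end month, stop date), at 23:59. Duration = E - onset. Lag = E - last dose, if E is after the last dose. Assumption: the stop date is the date of the last dose.

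**Step 1: how often the cap governs.** Take every first-dose date in 2024 (366) and every onset/end pair within Days 1 to 28 (28 × 29 / 2 = 406). This gives 366 × 406 = 148,596 combinations for each treatment length. The cap replaces month-end in 99.7% (5 calendar days) and 99.5% (6 days). Equal weighting shows the reach of the rule, not expected AE frequency.

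**Step 2: end before onset.** Every combination with onset on a day after the stop date ends before it starts. None does so with onset on or before the stop date. In this grid the affected pairs are 23 × 24 / 2 = 276 of 406 (68.0%) for 5 days, and 22 × 23 / 2 = 253 of 406 (62.3%) for 6 days.

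**Step 3: recorded month overwritten.** The imputed end falls outside the recorded end month in 46.1% (5 days) and 42.9% (6 days) of the grid.

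**Step 4: lag.** When the recorded end month is the stop month or later, lag = 23:59 minus the last-dose clock time. That is 15.0 h for a 09:00 dose, 6.0 h for 18:00 and 3.0 h for 21:00. The largest value, for a dose at 00:00, is 23.98 h.

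**Step 5: illustrative cases.** In A to C the last dose is 8 Nov 21:00 and the end is recorded only as November. At 12-h dosing the first dose is 8 Nov 21:00 - 9 × 12 h = 4 Nov 09:00. In D the last dose is 28 Nov 21:00 and the end is recorded only as December.

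| Case | Onset | True end | Imputed end | Duration: rule / truth | Lag: rule / truth |
|---|---|---|---|---|---|
| A | 9 Nov 06:00 | 11 Nov 12:00 | 8 Nov 23:59 | -6.0 / 54 h | 3.0 / 63 h |
| B | 7 Nov 12:00 | 14 Nov 12:00 | 8 Nov 23:59 | 36 / 168 h | 3.0 / 135 h |
| C | 4 Nov 12:00 | 5 Nov 12:00 | 8 Nov 23:59 | 108 / 24 h | 3.0 h / none |
| D | 28 Nov 12:00 | 1 Dec 00:00 at the earliest | 28 Nov 23:59 | 12 / at least 60 h | 3.0 / at least 51 h |

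In C the event ended 81 h before the last dose, yet the participant enters the lag summary. B and C err in opposite directions.

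**Step 6: negative durations among AChE-I events.** Onset must be within 12 h of the last dose, so this needs a last dose after 12:00. Assume, for scale only, that onset is uniform over the 9 × 12 + 12 = 120 h from first dose to 12 h after the last. For last-dose hour h, the share of AChE-I events with a missing end day that turn negative is max(0, h + 12 - 24) / 120. This is 0% up to 12:00, 6/120 = 5.0% at 18:00 and 9/120 = 7.5% at 21:00.

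**Step 7: does a floor suffice?** Raise E, where needed, to the later of the AE start date and the first day of the recorded month. D becomes 83.98 h with a lag of 74.98 h, and A becomes 17.98 h. Both values are now possible. B and C do not change.

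**The case against.** The case for leaving this alone is mainly one of scale. The documents do not say how many AEs will lack an end day. Sites call participants at Visits 6 and 7 and review unresolved AEs until Day 28, which gives chances to complete dates, although the remote callers do not ask about AEs directly. No hypothesis is tested, and listings show the date as captured. All of this stands and sets the priority.

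The lag result also depends on applying the 23:59 row to a substituted stop date. That is the literal reading. If the stop date and time were used instead, lag would be 0 and the participant would leave the lag summary. That does not reflect the true end either.

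A reader might infer more than the text supports:

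- **That AChE-I lags in general are corrupted.** Only a participant whose last AChE-I event lacks an end day is affected. Lags from complete dates are correct.
- **That most such AEs get a negative duration.** The 62% to 68% comes from an equally weighted grid over Days 1 to 28. AChE-I onset is confined to 12 h after the last dose, where the illustrative share is 0% to 7.5% at the last-dose times shown. The visible AE summary list in SAP 4.5.2 has no other duration table.
- **That the rule understates duration.** Case C overstates it, and the mix of cases is unknown.
- **That month-end imputation is always worse, or always better.** In A to C month-end errs more (+468, +396 and +612 h against -60, -132 and +84 h). With a last dose on 25 Nov 21:00 and a true end on 30 Nov 12:00, recorded as November, the cap errs by -108 h and month-end by +12 h. The ranking depends on where in the month treatment stops.

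**Conclusion.** The rule is wrong as written, because it can produce values that the recorded data rule out: an end before onset (A) or an end in a month other than the one recorded (D). No other rule in the visible SAP overrides it. For a participant whose last AChE-I event lacks an end day, the lag does not depend on when the event ended. If the recorded month is the stop month or later, she enters the lag summary even when the event ended on treatment.

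The lag conclusions assume that the stop date is the last-dose date and that 23:59 applies to it. The impossible dates in A and D do not need the 23:59 assumption.

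The reach is narrow: AChE-I duration and lag in SAP 4.5.2.1.3, and derived AE durations. TEAE counts, severity summaries and efficacy are unaffected. The number of affected events is unknown and may be small, and the net bias is undetermined. Minor priority.

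**What to change.** 1. **SAP 6.3.8:** state that an imputed AE end may not precede the AE start date/time or fall outside the recorded end month.
2. **SAP 4.5.2.1.3:** leave duration missing for an AChE-I event with an imputed end day. Leave lag missing for a participant with any such event, unless another of her AChE-I events has a complete end date that falls after the recorded end month of every such event. Report the numbers of events and participants excluded.

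The first change removes impossible derived durations but leaves cases such as B and C, so the two planned summaries need the second. Once the second is in place, the first changes no visible summary table, only derived AE durations. Leaving values missing is also what follows under the SAP when end day and month are both absent.

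The cost is a sentence or two in each section, an imputation flag, a comparison across each participant's AChE-I events for the lag condition, and a footnote count. Slightly fewer events and participants enter the two summaries. If longer events more often lack an end day, the remaining summary may understate duration. The exclusion counts show how many values were left out.
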